2.4 TABLE OF ENDPOINTS/OUTCOMES PILOT

	Objective	Outcome Measures	Summary method(s)
Primary	To determine the recruitment rate	Recruitment rate	
 Percentage recruited of all participants invited Number of individuals recruited per month

STUDY STAGE 1 and 2 (analysis inclusive of pilot):

	Objective	Outcome Measures	Summary method(s)
Primary	To estimate the proportion of PCs deemed resectable	Resectability rate	Percentage of PCs deemed resectable by the study MDT [compared between arms]
	To estimate the sensitivity of the Avantect test in detecting PC	Sensitivity	Percentage with PC diagnosed who have an Avantect “detected” result [within intervention arm]
	To estimate the specificity of the Avantect test in ruling out PC	Specificity	Percentage without PC diagnosed who have one or more Avantect “not detected” results and no Avantect “detected” results [within intervention arm]
Secondary	To determine the effect of the Avantect test on PC stage shift	Stage shift	Percentage of PCs diagnosed at stage I/II [compared between arms]
	To estimate the PPV of Avantect for detecting PC	PPV	Percentage with an Avantect “detected” result who have PC diagnosed [within intervention arm]

	To estimate the NPV of Avantect for ruling out PC	NPV	Percentage of individuals with no Avantect “detected” test results who have no diagnosis of PC [within intervention arm]
	To estimate the proportion of PCs that are resected	Resection	Percentage with PC who underwent resection [compared between arms]
Exploratory	To estimate the time from NOD diagnosis to PC diagnosis	Time to diagnosis	Kaplan-Meier curve Hazard ratio [within intervention arm]
	To estimate the overall survival of study participants	Overall Survival	Kaplan-Meier curve Hazard ratio [compared between arms]
	Assess the effect of the Avantect test on state anxiety over time	6-item STAI	T-test or non-parametric alternative if suitable [compared between arms]
	To investigate the performance characteristics for high-grade neoplasia	Sensitivity Specificity PPV NPV	As described above, but disease positive is defined as PC and/or high-grade mucinous cysts and non-cases defined as no pancreatic cancer or high-grade mucinous cysts. This will be repeated where high-grade mucinous cysts are considered as disease positive and PCs are excluded. [within intervention arm]

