4. OVERALL TRIAL DESIGN

A prospective, single blinded interventional randomised controlled multicentre study with a pilot followed by 2 stages of recruitment. Selected pre-existing conditions of interest, STAI, body measurements and blood samples will be collected at enrolment (Baseline (T0)), and at 6 months intervals (T1 and T2)). Three cancer and mortality registry searches will be undertaken by the SCTU study team to assess any cancer diagnosed and deaths during the Follow-up study period (T3) (Figure 1). Cancer registry database will be interrogated using any “C-codes and D-codes” available and data from any cancer type will be collected. Peer reviewed published data by the study team¹² has shown that the vast majority of pancreatic cancer patients are diagnosed, in NOD subjects, within 12 -18 months from type 2 diabetes diagnosis. Therefore, the study strategy is to test NOD patients at baseline (T0) (within 6 months from diabetes diagnosis) and thereafter at 6 and 12 months from T0 to ensure that the Avantect test is used in the period before pancreatic cancer symptoms usually present.

[figure not shown]

Figure 1: SAFE-D visit schedule figure

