7.6 TRIAL PROCEDURES

7.6.1 Timepoint T0

At enrolment visit participants will give informed consent to participate in the study and complete the following:

Sample collection

- 2x10 mL Streck® tubes
- 1x6 mL lithium heparin

Data collection at sites and transferred securely to SCTU

- NHS number
- Date of birth

Contact details (name, postal and email address) for a select number of participants (to be defined) who have consented to taking part in optional further research related to the health questionnaire.

Data collection at sites and entered into study database (Medidata RAVE)

- Height, weight and waist measurements
- 6-item STAI questionnaire
- Selected pre-existing conditions of interest, concomitant medications, family history, alcohol and smoking status

After T0 visit, participants will be randomised to either the control or intervention arm. GPs will be notified if patients under their care are taking part in the study but will remain blinded at this stage.

7.6.2 Timepoint T1 (6 months after T0):

Sample Collection:

- 2x10 mL Streck® tubes
- 1x6 mL lithium heparin

Data Collection:

- 6-item STAI Inventory questionnaire
- Selected pre-existing conditions of interest and concomitant medications
- Weight and waist measurements

7.6.3 Timepoint T2 (12 months after T0):

Sample Collection:

- 2x10 mL Streck® tubes
- 1x6 mL lithium heparin

Data Collection:

- 6-item STAI Inventory questionnaire
- Selected pre-existing conditions of interest and concomitant medications
- Weight and waist measurements

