Resection rate of PC. The analysis will be conducted by comparing resection between the intervention and control arms. With a sample size of 15,000, PC prevalence of 1%, and 2.5% lost to follow-up, there will be an expected 73 cases of PC in each arm. It is assumed that 5% of those deemed resectable will not undergo resection, for an expected rate of 38% (28/73) in the Intervention arm versus 13% (9/73) in the control arm. Resection rate will be considered successful if the proportion in the intervention arm is higher than the rate in the control arm at a one-sided p-value of 0.05.

For analyses of exploratory outcomes, the following applies:

Time-to-event outcomes (time to PC diagnosis and overall survival) will be analysed using a Cox regression model to determine the hazard ratio (and 95% confidence interval) between groups. This will be supported by a Kaplan-Meier plot for each group, median survival (and 95% confidence intervals), and estimates of 3-year survival (T0-T3) (alongside the difference in proportions and corresponding 95% confidence interval). The 6-item STAI will be analysed using a t-test or non-parametric suitable alternative if data are not normally distributed. Performance characteristics for high-grade neoplasia include sensitivity, specificity, PPV and NPV. They will be analysed as described

SAFE-D Clinical Performance Study Protocol Version 4, IRAS Ref: 326332 31-JUL-2025 Page 49 of 68

above, when high-grade neoplasia is also considered as Disease Positive, and when high-grade neoplasia alone (with the exclusion of pancreatic cancer) is considered as Disease Positive. Two-sided p-values will be presented for exploratory outcomes.

Unless otherwise stated, continuous data will be presented as means and standard deviations and analysed using a linear regression modelling framework. If data are skewed, medians and ranges will be presented. To analyse skewed data we will attempt to find a suitable transformation to allow a linear modelling approach. If this is not possible, we will explore whether another suitable parametric distribution fits the data. If not, a non-parametric approach, such as quantile regression, will be used. Binary data will be reported in terms of odds ratios and analysed using logistic regression modelling, unless otherwise stated.

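### The exploratory STAI analysis is fixed as a t-test with no score or visit named; a baseline-adjusted model of T1 and T2 fits the objective better at no cost

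*Protocol*

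**What the plan says.** The objective in the Protocol's section 2.4 table is: "Assess the effect of the Avantect test on state anxiety over time". The method beside it is "T-test or non-parametric alternative if suitable [compared between arms". Section 9.4 repeats the method: "The 6-item STAI will be analysed using a t-test", with a non-parametric alternative for non-normal data. Neither place says whether the test is applied to T1, to T2, to each in turn or to change from T0. Neither mentions baseline adjustment or a repeated-measures model.

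On timing, section 4 says that "STAI, body measurements and blood samples will be collected at enrolment (Baseline (T0)), and at 6 months intervals (T1 and T2", and the schedule in section 7.1 marks STAI at T0, T1 and T2. Section 7.6.1 places allocation afterwards: "After T0 visit, participants will be randomised to either the control or intervention arm". T0 STAI is therefore a true pre-randomisation covariate.

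Section 9.4 has a general rule for continuous outcomes: "Unless otherwise stated, continuous data will be presented as means and standard deviations and analysed using a linear regression modelling framework". Because a t-test is stated for STAI, the rule's opening condition takes STAI out of that default. For exploratory outcomes the section adds "Two-sided p-values will be presented for exploratory outcomes". No SD, effect size, power or success criterion is given for STAI.

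**The concern.** A two-sample t-test compares one number per person, whereas the objective is a pattern over time and up to three scores per person are planned. One test cannot use T1 and T2 together or estimate how the arm difference changes between them.

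That pattern matters in this design. STAI is completed at the visit, and the result of the sample drawn at that visit comes later (section 6.1). T1 STAI can therefore reflect only detected results from T0, and T2 STAI only those from T0 and T1. The share of the intervention arm that has been told a result thus differs between the two questionnaires.

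The second issue is precision. Only participants with a detected result are told (sections 7.5.2 and 7.8.2), so any whole-arm mean difference will be small, and a pre-randomisation score that could sharpen the comparison has no covariate role. What is at stake is the reading of an exploratory outcome. No go/no-go or success rule depends on it.

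**Working it through.** The protocol states no figure for STAI, so there is nothing to reproduce. The check compares the possible analyses.

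**Inputs from the protocol.** Intervention per-protocol n = 7,312 (section 9.2). Control n = 7,500, because all controls qualify (section 9.4) and the target is 7,500 per arm (section 9.2). Expected intervention participants with a detected result = 410 (section 9.4).

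**Assumptions, not in the documents.** Correlation r between T0 and follow-up STAI of 0.3, 0.5 or 0.7; equal SDs at the visits; two-sided alpha of 0.05; complete questionnaires unless stated.

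**Step 1: relative variance of the arm difference at one visit.** A t-test on the follow-up score is set to 1. A t-test on change from T0 has 2(1 − r). A baseline-adjusted linear model has 1 − r².

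| r | Follow-up t-test | Change t-test | Adjusted | Follow-up ÷ adjusted | Change ÷ adjusted = 2/(1 + r) |
|---|---|---|---|---|---|
| 0.3 | 1.00 | 1.40 | 0.91 | 1.10 | 1.54 |
| 0.5 | 1.00 | 1.00 | 0.75 | 1.33 | 1.33 |
| 0.7 | 1.00 | 0.60 | 0.51 | 1.96 | 1.18 |

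A simulation of 4,000 trials for each r gave 1.37, 1.00 and 0.59 for change and 0.90, 0.75 and 0.51 for the adjusted model, which agrees. The loss from a change score is smaller than that from a follow-up score when r is above 0.5, the same at 0.5, and larger below it. Neither t-test is more precise than adjustment at these values.

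**Step 2: absolute size.** SE of the follow-up t-test = √(1/7,312 + 1/7,500) = 0.0164 SD, so the 95% CI half-width = 1.96 × 0.0164 = 0.032 SD. Multiplying by √(1 − r²) gives 0.031, 0.028 and 0.023 SD. If only 60% returned the questionnaire (assumed), the half-width would be 0.042 SD, falling to 0.040, 0.036 and 0.030 SD.

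**Step 3: dilution.** Expected share told a result = 410/7,312 = 5.6%. Suppose being told raises STAI by 0.5 SD (assumed) and nobody else is affected. The arm difference is then 0.056 × 0.5 = 0.028 SD. Power is Φ(0.028/SE − 1.96): 40% for the follow-up t-test, and 43%, 50% and 67% with adjustment at r = 0.3, 0.5 and 0.7. This is optimistic, because the 410 includes detections at T2, which come after the last STAI.

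**The case against.** The strongest reply has four parts.

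- **The text is silent on the score.** A reader might infer that the plan ignores baseline. The documents do not support that: a t-test on change from T0 is an ordinary reading of an objective about change over time, and it uses the baseline. Separate t-tests at T1 and T2 would also describe the arm difference at each visit. This stands, and it is why the precision loss is given for both scores.
- **Such detail usually belongs in the SAP.** Section 9.4 promises a full SAP and gives only main features. Score, visit and covariates could properly wait for it. But the protocol does not leave the method open: it names a t-test in two places and thereby removes STAI from its own regression default. The point concerns that stated choice.
- **Nothing stated is invalid.** Under 1:1 randomisation with complete data the t-test is an unbiased comparison, the outcome is exploratory and no power is claimed. This stands in full.
- **The gain is small and does not cure dilution.** A reader might take a variance cut of 25% to 49% (r = 0.5 to 0.7) as the headline. It assumes a follow-up-only comparator and correlations that are not in the documents. In the illustration above, adjusted power is still only 43% to 67%, because the whole arms are still being compared. This also stands.

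**Conclusion.** The point holds as a minor, free improvement. The protocol fixes a valid but limited method for STAI, leaves the score and visit unnamed, and so does not match an objective framed over time. The mismatch with the objective is the stronger half.

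The precision half is right in direction for any positive r, but modest in absolute terms: the half-width drops by between 0.001 and 0.009 SD from 0.032 SD over r = 0.3 to 0.7. Those figures rest on the assumed r, equal SDs, complete questionnaires and a follow-up-score t-test.

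Two stronger readings should be resisted. The t-test is not biased, and adjustment would not make a diluted whole-arm comparison well powered. A null result from either analysis should not be read as reassurance about those who were told a result. STAI at T0 is scheduled for every participant, but the schedule does not guarantee completeness.

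**What to change.** In sections 2.4 and 9.4, replace the t-test with a linear mixed model of STAI at T1 and T2 with arm, visit, arm-by-visit and T0 STAI, reporting the arm difference and 95% confidence interval at each visit. Baseline-adjusted linear regression at each named visit is an acceptable simpler form. Either brings STAI back within section 9.4's linear-model default, whose provisions for skewed data would then apply. The SAP should say how a missing T0 score is handled. It should also note that participants with a cancer diagnosis on imaging discontinue study visits (section 7.12), so some of those told a result will lack later scores. A mixed model uses whatever visits remain, but it only mitigates that loss.

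The cost is wording in two places. The planned data already suffice, and neither the sample size nor any decision rule changes.

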7.8.2. Not detected

Participants in the intervention arm who have an Avantect “not detected” test result will not be informed of their result and will continue with study schedule of observations and procedures.

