7.9.3 Abnormal imaging outcome showing pancreatic cystic lesion

For abnormal imaging outcomes showing a pancreatic cystic lesion, European or local guidelines will be followed.

IPMN or Mucinous cystic neoplasms (MCN) that, after surgical and histopathological evaluation, show a high-grade dysplasia phenotype will be considered as pancreatic cancer¹². Otherwise, low grade dysplasia and other non-mucinous cystic lesions will not be considered as pancreatic cancer.

Participants in the intervention arm with Avantect “detected” test results and for whom pancreatic cysts have been found by MRI/CT, and surveillance has been recommended, will continue study visits as scheduled and will be considered as non pancreatic cancer outcome regardless of the size of the cyst until proven otherwise by pathological examination (Appendix III)

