9.3 STUDY TIMEPOINTS

There will be three timepoints for blood collection: at baseline (T0), 6 months +/- 2 weeks post-baseline (T1), and 12 months +/- 2 weeks from baseline (T2). For each study timepoint, the Avantect test will be conducted. For samples collected from participants assigned to the intervention arm, the Avantect test will be assessed as soon as possible within 14 business days of receipt of samples in the analysing laboratory at ClearNote Health. Those with positive test results (test result = Avantect “detected”) in the intervention arm will undergo diagnostic pancreas imaging. Samples collected from participants assigned to the Control arm will be stored for potential future Avantect testing or future research.

The study design comprises a pilot and two study stages:

- Stage 1 Analysis will be carried out 6 months after the T1 visit for 3,200 participants in the intervention arm. Only participants followed up for a minimum of 6 months after the T1 visit in the intervention arm will be included in this analysis.
- Stage 2 Analysis will be carried out after 3-year follow-up data has been collected for all 15,000 participants.

In addition, during the study annual readouts will be provided to the data monitoring committee to monitor study progress and inform on decisions to continue or stop the study.

The diagnostic performance of the Avantect test results will be summarised according to the pancreatic cancer diagnoses collected by the point of analysis. The stage shift, and resection rate of pancreatic cancer will be summarised by arm. For this purpose, a positive test at any timepoint will be considered a ‘positive prediction’ e.g., if a participant has a negative result at T0, but a positive result at T1, their overall prediction will be considered as at-risk of pancreatic cancer.

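### The exploratory sensitivity for high-grade neoplasia is biased upward by partial verification, because study imaging follows only a 'detected' result

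*Protocol*

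**What the plan says.** Section 9.4 states: "Performance characteristics for high-grade neoplasia include sensitivity, specificity, PPV and NPV". The analysis is run once with high-grade neoplasia added to PC and once "when high-grade neoplasia alone (with the exclusion of pancreatic cancer) is considered as Disease Positive". The endpoint table in Section 2.4 agrees: "This will be repeated where high-grade mucinous cysts are considered as disease positive and PCs are excluded". Both place it in the intervention arm.

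The procedures that decide who is found to have such a lesion are these:

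- **Imaging.** Section 9.3 says that those with a positive test "in the intervention arm will undergo diagnostic pancreas imaging". Section 7.8.1 sets up the referral.
- **No work-up after 'not detected'.** Under Section 7.8.2 these participants "will not be informed of their result and will continue with study schedule of observations and procedures". The schedule in Section 7.1 contains repeat tests and record review at T1 and T2, but no imaging.
- **How high grade is established.** Section 7.9.3 refers to cysts that "after surgical and histopathological evaluation, show a high-grade dysplasia phenotype will be considered as pancreatic cancer". In the same section, a cyst under surveillance in a 'detected' participant stays a non-PC outcome until pathology shows otherwise.
- **Passive capture.** Section 7.6.4 requests registry data for ICD-10 C00-D48 with histology. Section 7.11 collects pathology and imaging on incidental findings when available.
- **Reference method.** Section 7.10 defines it for PC only.

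Known pancreatic cysts are excluded at entry (Section 5.4), so the target lesions are undiagnosed at baseline. The protocol neither verifies a sample of 'not detected' participants, nor corrects for partial verification, nor qualifies the high-grade figures.

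**The concern.** Sensitivity needs a count of diseased people that does not depend on the test result. Here the chance of being counted as diseased depends on it directly. A 'detected' result leads to pancreatic imaging and possibly to surgery and pathology. A participant who is 'not detected' at all three visits has only routine care, record review and registry coding. A lesion missed by the test tends to drop out of the sensitivity denominator and be counted as a true negative.

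For PC the protocol offers an answer. Section 4 says that most cancers in people with new-onset diabetes are diagnosed within 12 to 18 months of the diabetes diagnosis, so a missed cancer should reach the registry. It makes no such argument for cysts, which Section 1.2 describes as precursors, only some of which may become malignant.

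Section 1.2 already suggests that the test may pick up some neoplastic cysts and stresses finding them early. A high sensitivity from a prospective randomised study would look like confirmation, even if true sensitivity were low. Because the gap lies in the study procedures, a later analysis plan cannot recover the missing information from the planned data.

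**Working it through.** **Plan's own figures.** None is given for high-grade neoplasia. The PC table in Section 9.2, whose method is reused, reproduces:

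- 7,500 x 0.975 = 7,312 per protocol; x 1% = 73 PC; 7,312 - 73 = 7,239 without PC
- true positives 0.65 x 73.1 = 47.5 (48); false positives 0.05 x 7,239 = 362; true negatives 0.95 x 7,239 = 6,877
- NPV 6,877/6,902 = 99.6%

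**Inputs not in the documents (assumed).** High-grade prevalence 0.2% to 1%; true sensitivity S, mainly 20%; v1 = chance that an existing lesion is diagnosed after 'detected'; v0 = the same chance after 'not detected' throughout. Specificity is taken as 95%, as for PC.

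**Cyst-only sensitivity.** Observed sensitivity = S·v1 / (S·v1 + (1 - S)·v0). Prevalence cancels. For S = 20%:

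| | v0 = 0.05 | v0 = 0.10 | v0 = 0.20 |
|---|---|---|---|
| v1 = 1 | 0.20/0.24 = 83% | 0.20/0.28 = 71% | 0.20/0.36 = 56% |
| v1 = 0.3 | 0.06/0.10 = 60% | 0.06/0.14 = 43% | 0.06/0.22 = 27% |

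Every cell exceeds 20%. The ratio equals S only when v1 = v0. Incomplete pathology after 'detected' shrinks the bias but does not reverse it while v1 > v0. A test with no information (S = 5% at specificity 95%) would show 0.04/(0.04 + 0.0475) = 46% at v1 = 0.8 and v0 = 0.05.

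**Combined PC-or-high-grade sensitivity.** Take prevalence 0.5% of 7,239 (36.2 lesions), S = 20%, v1 = 0.8, v0 = 0.05, and PC fully ascertained with 48 of 73 detected:

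- true: (48 + 7.2)/(73 + 36.2) = 50.6%
- observed: (48 + 5.8)/(73 + 5.8 + 1.4) = 67.0% (from unrounded counts)

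At 0.2% prevalence the same inputs give 58.2% true and 66.3% observed.

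**NPV (PC excluded, S = 20%).** At 0.2% prevalence there are 14.5 lesions, of which 11.6 are missed. Test-negatives are 0.95 x (7,239 - 14.5) + 11.6 = 6,875. The largest possible inflation (v0 = 0) is 11.6/6,875 = 0.17 percentage points. At 1% prevalence it is 57.9/6,866 = 0.84 points. Specificity moves by less than 0.5 points across the range examined.

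**Case definition.** Under Section 7.9.3, a cyst confirmed as high grade at surgery is PC. Under Sections 2.4 and 9.4, the cyst-only analysis removes PC and keeps high-grade cysts as cases. Applied together, these rules could leave no cases, and the cyst-only sensitivity would then be undefined.

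**The case against.** The strongest reply is that the figures rest entirely on assumed rates and that ascertainment after 'not detected' is low rather than absent. Participants are retested at T1 and T2, and a later positive leads to imaging and counts as a positive prediction. Records are reviewed, incidental pathology is collected, and the registry request covers D-codes with histology. All this stands, so v0 is above zero and its size is unknown. It does not remove the bias, because a 'detected' participant has these routes and imaging as well.

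Surveillance without pathology also means that v1 can be well below 1, so the 56-83% row is a best-verification case. That is correct, and the 27-60% row allows for it.

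Section 2.4 already words sensitivity in terms of diagnosed disease, and the outcome is exploratory, with no success threshold, power claim or stop-go role. Both points lower the stakes. But the figure is still presented as a performance characteristic of the test, with no caveat.

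Three stronger readings are tempting but unsupported:

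- A reader might infer that observed sensitivity must be close to 100%. That needs v0 near zero, and incidental capture makes it lower.
- A reader might infer that NPV is seriously distorted. It would look excellent mainly because prevalence is low.
- A reader might infer that high-grade cysts stay silent for years. The protocol does not say so. The argument needs only the difference in work-up.

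**Conclusion.** The concern holds for sensitivity. The planned high-grade figure mixes the test's ability to detect a lesion with the extra chance of diagnosis that a 'detected' result brings. The direction is upward whenever v1 > v0, which the procedures make likely. The size cannot be fixed, because the documents give neither v1 nor v0 and the planned data do not identify v0. In the illustration, a true 20% becomes 56-83% with complete verification of detected lesions and 27-60% with 30% verification. The combined sensitivity is affected less, and NPV inflation is small in absolute terms.

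A reader might also infer that this invalidates the co-primary PC sensitivity. The documents do not support that: missed invasive cancers are expected to surface and reach the registry. The exposure there is limited to any high-grade cysts counted as PC under Section 7.9.3, in a number the protocol does not give.

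The conflict between Section 7.9.3 and Sections 2.4 and 9.4 is a separate defect and needs no assumptions.

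**What to change.** In Sections 2.4 and 9.4:

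1. Do not present the cyst-only sensitivity and NPV as test accuracy. Drop both, or keep the sensitivity figure relabelled as the proportion of clinically diagnosed high-grade lesions with a 'detected' result.
2. Keep the combined PC-or-high-grade analysis, with the corresponding label and a statement that high-grade lesions in 'not detected' participants are not systematically verified. Deleting it would be unsafe while Section 7.9.3 counts some of these lesions as PC.
3. Report PPV and yield per 1,000 tested, noting that surveilled cysts without pathology leave PPV incompletely verified. Add a between-arm comparison of diagnosed high-grade neoplasia per randomised participant, using the registry D-codes already requested. This measures the effect of testing on diagnosis and needs no disease status for undiagnosed people.
4. Reconcile Section 7.9.3 with Sections 2.4 and 9.4, so that a surgically confirmed high-grade IPMN or MCN has one stated status in each analysis, including the co-primaries.

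The cost is protocol and SAP wording. One or two exploratory accuracy figures are lost or renamed. No new imaging or data are needed.
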